7.10.2. Six-minute Walk Test

Exercise tolerance will be evaluate during the 6MWT according to ATS guidelines (ATS 2002) (Appendix B) as per the schedule of events (Appendix A). If possible, 6MWT

should be the last efficacy assessment completed, by the subject. If it is not possible to complete the 6MWT last, then allow a 30-minute recovery time before continuing with the next efficacy assessment. During the open-labeled extension, subjects will have 6MWT measured every twelve weeks.

7.10.3. **High-resolution Computed Tomography**

High-resolution Computed Tomography (HRCT) will be performed at the Baseline and Weeks 28, and weeks 76 and 128 visits for subjects continuing treatment in the extension.

Spirometry will be performed at selected sites to ensure that full inspiration HRCT is at Total Lung Capacity (TLC).

HRCT is to be performed with the subject in the supine position and at full inspiration. Contiguous CT volumetric acquisition will be obtained according to a specified protocol. HRCT scans will be compared using a standardized reading protocol and software to assess treatment-related changes in lung fibrosis.

7.10.4. **Patient Reported Outcomes**

Kings Brief Interstitial Lung Disease questionnaire (K-BILD) (Patel, Siegert et al.) (Appendix D) is a disease specific questionnaire validated to look at the health status of subjects with a variety of forms of interstitial lung disease (ILD). It consists of 15 items. The K-BILD questionnaire will be performed as per the schedule of events (Appendix A). If possible, the questionnaire should be the first assessment completed by the subjects.

Leicester Cough Questionnaire (Birring, Prudon et al. 2003) (Appendix E) a self-completed health related quality of life measure of chronic cough. The LCQ total score ranges from 3 to 21 and from 1 to 7 for physical, psychological and social domains; a higher score indicates a better health-related quality of life. The LCQ questionnaire will be performed as per the schedule of events (Appendix A). If possible, the questionnaire should be the first assessment completed by the subjects.

7.10.5. **Pentraxin-2 Levels**

Blood samples for determination of pentraxin-2 levels are to be collected pre-dose as per the schedule of events (Appendix A).

7.10.6. **Anti-Pentraxin 2 antibodies / Anti-Drug Antibodies (ADA)**

Blood samples for determination of ADA levels are to be collected pre-dose as per the schedule of events (Appendix A).

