Change in Patient Reported Outcomes will be assessed based on the King's Brief Interstitial Lung Disease Questionnaire (K-BILD) and Leicester Cough Questionnaire (LCQ). Descriptive statistics for raw values and change from Baseline to each visit in total score of both questionnaire will be computed by treatment group. Differences between treatment groups in change from baseline to week 28 for total score of each questionnaire will be tested using a similar approach to the one used for the primary analysis (see section 5.2.5.1). These analysis will be performed on both the ATS and the PP data sets (Statistical tables 14.2.20.1.1 to 14.2.20.3.2 and 14.2.21.1.1 to 14.2.21.3.2, Figures 14.2.17.1 to 14.2.17.2 and 14.2.18.1 to 14.2.18.2). All results of K-BILD and LCQ will be reported in Listings 16.2.6.4.1 to 14.2.6.4.2.2 and 16.2.6.5.1 to 16.2.6.5.2.2.

For the LCQ, in addition to the above approach, frequency of patients with changes below or above 1.3 (identified as the minimal important difference) will be tabulated by treatment groups at week 4, 8, 12, 16, 20, 24 and 28 (Statistical table 14.2.21.4.1 and 14.2.21.4.2).

Descriptive statistics for raw values at each visit and change from baseline to each visit in anti-Pentraxin-2 antibodies measurements will be computed by treatment group. This analysis will be performed on both the ATS and the PP dataset (Statistical 14.2.22.1.1 to 14.2.22.2.2). Individual measurements of anti-pentraxin-2 antibodies will be reported in Listing 16.2.6.8.

EO3: To assess the use of quantitative imaging in IPF

The correlation between baseline FVC [% predicted], DLCO (corrected for Hb, [% predicted]), TLC by nitrogen washout, PROs and 6MWD and total lung volume and volume of parenchymal features on HRCT (in ml and % of total lung volume) representative of ILA by quantitative imaging, as well as change from Baseline to Week 28 in FVC [% predicted], DLCO (corrected for Hb, [% predicted]), TLC by nitrogen washout, PROs and 6MWD and change from Baseline to Week 28 in total lung volume and volume of parenchymal features on HRCT (in ml and % of total lung volume) representative of ILA will be computed. This analysis will be performed on both the ATS and the PP dataset (Statistical tables 14.2.23.1.1 to 14.2.23.1.2).

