6.3 Changes in exploratory efficacy analyses

All exploratory efficacy analysis will be performed on both the ATS and the PP.

It was initially planned (EO1) to evaluate the efficacy and estimate the size of effect of PRM-151 relative to placebo in change from baseline to weeks 4, 8, 12, 16, 20, and 24 in FVC % predicted, FVC in ml and 6 minute walking distance using mixed models with random intercepts. To obtain a better description of individual variability, both random intercepts and random slopes will be used.

The following not initially planned exploratory analysis were added (see section 5.2.5.3 for details):

- To assess the use of quantitative imaging in IPF (E03)
- To explore the relationship between Anti-Pentraxin 2 antibodies (ADA) presence and level of FVC [% predicted] in time
- To explore PK/PD relationship.
- To explore relationship between Pentraxin-2 levels and ADA
- To explore acute exacerbations
- To explore time variations in FVC % predicted separately in patient (i) on stable dose of pirfenidone and (ii) on a stable dose of pirfenidone.

7 Software documentation

All summaries and statistical analyses will be generated using SAS version 9.4 or higher.

8 Derived data

Derived variable	Derivation algorithm
Change from baseline to visit V (continuous)	Change from baseline of variable $X = X_{(Visit V)} - X_{(Baseline)}$ 
 ○ Negative values indicate a decrease in X ○ Positive values indicate an increase in X

Percent change from baseline to visit V (continuous)	Percent change from baseline of variable X= $100 * [X_{(Visit V)} - X_{(Baseline)}] / X_{(Baseline)}$ 
 ○ Negative values indicate a decrease in X ○ Positive values indicate an increase in X
Treatment compliance	Continuous variable: The compliance C_i for patient i will be computed according to: $C_i = \frac{D_i^t * 100}{D_i^p}$ 
where D_i^p mg is the total amount (mg) of IP prescribed to patient i and D_i^t is the total amount (mg) of IP actually taken by the patient during the study i.e., before the end of study for patient i.

Treatment compliance (categorical)	Categorical variable with three modalities: 
 • $C_i < 80\%$ • $80\% \leq C_i < 120\%$ • $C_i \geq 120\%$

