14.2.19.2.3.1.a to 14.2.19.2.3.2.a	(EO2) Exploratory analyses: HRCT image analysis (total lung volume) - SVC breathhold at CT scanning $< 90\%$ of SVC supine - Anova table
14.2.19.2.3.1.b to 14.2.19.2.3.2.b	(EO2) Exploratory analyses: HRCT image analysis (total lung volume) - SVC breathhold at CT scanning $< 90\%$ of SVC supine - Model parameter estimates
14.2.19.2.3.1.c to 14.2.19.2.3.2.c	(EO2) Exploratory analyses: HRCT image analysis (total lung volume) - SVC breathhold at CT scanning $< 90\%$ of SVC supine - Least Square Means for change I nbaseline
14.2.20.1.1 to 14.2.20.1.2	(EO2) Exploratory Efficacy Analysis: King's Brief Interstitial Lung Disease Questionnaire (K-BILD) - raw values at each visit
14.2.20.2.1 to 14.2.20.2.2	(EO2) Exploratory Efficacy Analysis: King's Brief Interstitial Lung Disease Questionnaire (K-BILD) - change from baseline to each visit
14.2.20.3.1.a to 14.2.20.3.2.a	(EO2) Exploratory Efficacy Analysis: King's Brief Interstitial Lung Disease Questionnaire (K-BILD) - Anova table
14.2.20.3.1.b to 14.2.20.3.2.b	(EO2) Exploratory Efficacy Analysis: King's Brief Interstitial Lung Disease Questionnaire (K-BILD) - Model parameter estimates
14.2.20.3.1.c to 14.2.20.3.2.c	(EO2) Exploratory Efficacy Analysis: King's Brief Interstitial Lung Disease Questionnaire (K-BILD) - Least Square Means by stratum at each visit
14.2.20.3.1.d to 14.2.20.3.2.d	(EO2) Exploratory Efficacy Analysis: King's Brief Interstitial Lung Disease Questionnaire (K-BILD) - Least Square Means for change from baseline at each visit
14.2.21.1.1 to 14.2.21.1.2	(EO2) Exploratory Efficacy Analysis: Leicester Cough Questionnaire (LCQ) - raw values at each visit
14.2.21.2.1 to 14.2.21.2.2	(EO2) Exploratory Efficacy Analysis: Leicester Cough Questionnaire (LCQ) - change from baseline to each visit
14.2.21.3.1.a to 14.2.21.3.2.a	(EO2) Exploratory Efficacy Analysis: Leicester Cough Questionnaire (LCQ) - Least Square Means
14.2.21.3.1.b to 14.2.21.3.2.b	(EO2) Exploratory Efficacy Analysis: Leicester Cough Questionnaire (LCQ) - Anova table
14.2.21.3.1.c to 14.2.21.3.2.c	(EO2) Exploratory Efficacy Analysis: Leicester Cough Questionnaire (LCQ) - Model parameter estimates

14.2.21.4.1 to 14.2.21.4.2	(EO2) Exploratory Efficacy Analysis: Leicester Cough Questionnaire (LCQ) - frequency of patients with changes below or above 1.3 at each visit
14.2.22.1.1 to 14.2.22.1.2	(EO2) Exploratory Efficacy Analysis: anti-Pentraxin-2 antibodies - raw values at each visit

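### The LCQ frequency table has a single cut at 1.3, so it cannot show how many patients had an important worsening of cough

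*SAP*

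**What the plan says.** SAP 5.2.5.3, under EO2, adds one frequency table for the LCQ: "frequency of patients with changes below or above 1.3 (identified as the minimal important difference) will be tabulated by treatment groups", at Weeks 4, 8, 12, 16, 20, 24 and 28. The list of tables in SAP 9.1 (14.2.21.4.1 to 14.2.21.4.2) repeats the same two categories: "frequency of patients with changes below or above 1.3 at each visit". Neither place gives a sign for 1.3 or a cut at -1.3, and neither assigns a change of exactly 1.3 to a cell.

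The direction has to be pieced together from elsewhere. SAP section 8 defines change as the visit value minus baseline and adds "Negative values indicate a decrease in X". Protocol 7.10.4 gives the scale, "The LCQ total score ranges from 3 to 21 and from 1 to 7 for physical, psychological and social domains", and its direction: "a higher score indicates a better health-related quality of life".

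The table supplements other LCQ analyses in the same part of SAP 5.2.5.3. These include "Descriptive statistics for raw values and change from Baseline to each visit in total score of both questionnaire will be computed by treatment group" and a model-based comparison: "Differences between treatment groups in change from baseline to week 28 for total score of each questionnaire will be tested". Individual LCQ results are listed (Listing 16.2.6.5).

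**The concern.** A frequency table at a minimal important difference is meant to show what a mean cannot: how many patients changed by an amount that matters, and in which direction. This table supports the objective on disease-related symptoms. Protocol 1.1 describes IPF as progressive and names cough among the symptoms that appear over time, so worsening is at least as relevant as improvement.

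With one cut, a patient who loses 5 points and a patient who gains 1.2 fall in the same cell. The two arms could have identical tables while one has twice as many patients with important deterioration. The SAP does not treat lung function this way. Under SO6 in SAP 5.2.5.2, decline, increase and stability of FVC are tabulated as separate outcomes.

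**Working it through.** **Inputs.** From the documents: threshold 1.3 (SAP 5.2.5.3), signed change (SAP section 8), LCQ total 3 to 21 with higher better (Protocol 7.10.4), and planned arms of 78 and 39 (SAP 2.3.2). Not in the documents: the mean and SD of LCQ change, and the baseline LCQ distribution. These are assumed below.

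**1. Scale.** Three domains scored 1 to 7 give 3 × 1 = 3 and 3 × 7 = 21, which reproduces the stated range. The largest possible loss is 3 - 21 = -18.

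**2. What each cell contains.**
- Signed reading: the lower cell runs from -18 up to 1.3. It contains important worsening (-18 to -1.3) and no important change (-1.3 to +1.3). The upper cell contains improvement only.
- Absolute reading: the lower cell contains no important change, and the upper cell pools improvement with worsening.
- On both readings a change of exactly 1.3 belongs to neither cell.

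**3. How much mixing there could be (illustration, signed reading).** Take change as normal with mean m and SD s. The worsened fraction is W = Φ((-1.3 - m)/s), the lower cell is B = Φ((1.3 - m)/s), and the share of interest is W/B. For m = 0 and s = 2, W = Φ(-0.65) = 0.258, B = Φ(0.65) = 0.742 and W/B = 0.35. Shares for other assumed values:

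| Assumed SD | mean -1 | mean 0 | mean +1 |
|---|---|---|---|
| 1.5 | 44.9% | 23.9% | 10.8% |
| 2 | 50.3% | 34.7% | 22.3% |
| 3 | 59.1% | 49.8% | 41.1% |
| 4 | 65.5% | 59.4% | 53.3% |

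The range is about 11% to 66%. The normal model is unbounded and ignores the limits of the scale, so these figures show only that the mixing could be small or large.

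**4. Identical tables, different worsening.** Let both arms have 74.2% in the lower cell. One arm has 25.8% worsened and 74.2 - 25.8 = 48.4% unchanged. The other has 2 × 25.8 = 51.6% worsened and 74.2 - 51.6 = 22.6% unchanged. The planned table is the same for both.

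**5. Headroom.** 21 - 1.3 = 19.7, so a patient whose baseline is above 19.7 cannot gain 1.3. That is the top 1.3/18 = 7.2% of the scale range. If 5% to 30% of patients started there (assumed), the counts would be 0.05 × 78 = 3.9 to 0.30 × 78 = 23.4 on PRM-151, and 0.05 × 39 = 1.95 to 0.30 × 39 = 11.7 on placebo.

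**6. Precision of a worsened-patient comparison.** With 25.8% worsened in both arms and all 117 patients observed, the standard error is √(0.258 × 0.742 × (1/78 + 1/39)) = 0.086. The 90% half-width is 1.645 × 0.086 = 0.14, or about 14 percentage points.

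**The case against.** The strongest reply is that little depends on this table. The LCQ is an exploratory endpoint and the table is a descriptive addition. No test, error rate, sample size or planned conclusion rests on it. That stands, and it sets the weight of the point.

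A reader might infer that the plan hides worsening of cough altogether. The documents do not support that. Signed change in total score is summarised at every visit, and SAP 5.1.1 requires mean, SD, median, quartiles and extremes. If the lower quartile of change is -1.3 or below, at least about a quarter of that arm worsened by 1.3 or more. There is also a Week 28 comparison, and individual scores are listed. What is missing is a direct count of worsened patients by arm.

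A reader might also take the signed reading as certain. It is the more natural one, given SAP section 8, but SAP 5.2.5.3 does not state it. The safe statement is that the categories are under-specified and that both readings fail in the same respect.

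A third inference is that patients near the top of the scale are wrongly declared non-responders. The SAP defines no responder; such patients are simply tabulated as below 1.3. The limit of 19.7 is correct, and Protocol 5.1.1 and 5.1.2 set no cough requirement. However, no baseline LCQ distribution is given, and baseline LCQ by arm is already tabulated (14.1.11.2.1 to 14.1.11.2.2). The ceiling is worth a footnote at most.

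Finally, a mean of 0 with SDs of 2 to 4 would give 35% to 59%, which could be mistaken for an estimate. Neither value is in the documents, and modest changes to them widen the range to 11% to 66%.

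**Conclusion.** The point holds as a minor one. Table 14.2.21.4 as specified cannot show important worsening of cough. On the signed reading, worsened patients share a cell with unchanged patients; on the absolute reading, they share one with improvers. This follows from the documents' own definitions and needs no assumption about the data.

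The size of the effect on the table is unknown, because no SD of LCQ change is given; the illustrative range only brackets what is possible. The consequence is confined to one exploratory table, and the other planned LCQ outputs recover part of the information. The primary analysis is unaffected.

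**What to change.** In SAP 5.2.5.3 and in the titles of tables 14.2.21.4.1 and 14.2.21.4.2, replace the two categories with three at each visit:
- improved: change of +1.3 or more;
- no important change: above -1.3 and below +1.3;
- worsened: change of -1.3 or less.

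This settles the sign and places a change of exactly 1.3. State that 1.3 is applied in both directions as an assumption, since the SAP gives the minimal important difference without a direction. At Week 28, give the between-arm differences in improved and in worsened with 90% confidence intervals, the level SAP 5.1.2 sets for exploratory endpoints. Name the interval method, because SAP 5.1.1 names one only for single proportions. The intervals will be wide (about ±14 points in the illustration) and should be read as descriptive.

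Optionally, footnote the number per arm with a baseline above 19.7. A separate row restricted by baseline is not needed.

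The cost is a short SAP edit, one more row at each of seven visits in two tables, and two differences with intervals. No new data are needed. Make the change before unblinding, because a worsened category added afterwards would be post hoc.

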1.5. Risk/Benefit Assessment

PRM-151, a recombinant form of an endogenous human protein, has been well tolerated in preclinical toxicology studies and Phase 1 and 2 clinical studies, and has shown an early trend towards efficacy in subjects with IPF. Based on encouraging Phase 1 data in subjects with IPF, PRM-151 has the potential to be a safe, disease modifying treatment for a broad spectrum of fibrotic diseases, including IPF.

PRM-151 represents the recombinant version of an endogenous human serum protein, and as such was predicted to have a very favorable safety index. This prediction has been confirmed in multiple preclinical and clinical studies to date. Two Phase 1 studies of

PRM-151 administered IV to normal volunteers and IPF subjects have been completed, with no SAEs reported and no other safety signals seen. The single ascending dose study (PRM151A-11EU) tested dose levels as high as 20 mg/kg. The multiple ascending dose study (PRM151F-12GL) demonstrated that PRM-151 administered by 30-minute IV infusion on Days 1, 3, 5, 8 and 15 at up to 10 mg/kg was safe and well tolerated in subjects with IPF, with no SAEs noted in 57 days; similar types and number of TEAEs were reported in both PRM-151 and placebo treated subjects. Safety data from 27 subjects with MF, including 24 weeks of safety data in 20 subjects and an additional 12 weeks of safety data in 10, confirms the excellent safety profile of PRM-151 to date. Most adverse events have been Grade 1 or 2 and unrelated to PRM-151, and 5 possibly related SAEs, including one death, have been reported in a group of older subjects (median age 67 years) with a serious, life threatening disease.

Risks associated with PRM-151 are inherent in its being the recombinant form of a naturally occurring human protein, and consist of potential development of anti-drug antibodies and infusion reactions. PRM-151 has an endogenous counterpart, and, therefore, anti-drug antibodies could develop that could potentially affect the efficacy of PRM-151 treatments in addition to having the potential to cross-react with endogenous hPTX-2. Anti-drug antibodies were detected in 3 subjects in the MF trial, with no apparent impact on pharmacokinetics, safety, or efficacy. Two subjects had mild infusion reactions which were easily managed and prevented in the one subject that was rechallenged; anti-drug antibody was detected in one of them.

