5.2.5.3 Exploratory efficacy analyses

For all exploratory efficacy endpoints, the analyses will be based on observed data only *i.e.*, no data will be imputed.

EO1: To evaluate the efficacy and estimate the size of effect of PRM-151 relative to placebo in change from baseline to weeks 4, 8, 12, 16, 20, and 24 in FVC % predicted, FVC in ml and 6 minute walking distance, pooling subjects on a stable dose of pirfenidone or nintedanib with subjects not on other treatment for IPF and separately in subjects on a stable dose of pirfenidone or nintedanib and in subjects not on other treatments for IPF.

A model similar to that of the primary analysis (see section 5.2.5.1) but with the addition of random slopes will be used to evaluate on both the ATS and the PP data sets the efficacy and estimate, pooling subjects on a stable dose of pirfenidone or nintedanib with subjects not on other treatment for IPF and separately in subjects on a stable dose of pirfenidone or nintedanib and in subjects not on other treatments for IPF, the size of effect of PRM-151 relative to placebo in time variations in FVC [% predicted] (Statistical tables 14.2.13.1 to 14.2.14.2.2, Figures 14.2.10.1 to 14.2.11.2.2), FVC [ml] (Statistical tables 14.2.15.1 to 14.2.16.2.2, Figures 14.2.12.1 to 14.2.13.2.2) and 6MWD (Statistical tables 14.2.17.1 to 14.18.2.2, Figures 14.2.14.1 to 14.2.15.2.2). The individual slopes and intercepts will be listed (Listings 16.2.6.10 to 16.2.6.12). Statistical inference (90% CI and p-values) on the slope difference between treated and placebo groups will be reported.

EO2: To assess the impact of PRM-151 on disease related symptoms and quantitative imaging.

Mean change from Baseline to Week 28 in total lung volume and volume of parenchymal features (see section 8) on HRCT (in ml and % of total lung volume), representative of interstitial lung abnormalities (ILA) will be computed, comparing PRM151 vs. placebo (separately) in patients with SVC breathhold at CT scanning $\geq 90\%$ of SVC supine, with a similar approach to the one used

for the primary analysis (statistical tables 14.2.19.1.1.1 to 14.2.19.2.3.2, Figure 14.2.16.1.1 to 14.2.16.2.2).

For all categories of lung features (including PVV), the change from baseline to week 28 in volume of a given lung feature (both in ml as well as in % of total lung volume) will be computed in subjects treated with PRM-151 and placebo, depending on the completeness and usability of the obtained data.

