The relationship between Anti-Pentraxin 2 antibodies (ADA) presence and level of FVC [% predicted] in time will be studied by modelling the influence of presence/absence (and/or level) of ADA in the repeated measures mixed model used for the primary efficacy analysis (see section 5.2.5.1) and if relevant using non-parametric spline functions. The most parsimonious model will be chosen on the basis of the AIC (Statistical table 14.2.25.1 and 14.2.25.2).

Additional exploratory analysis: Baseline characteristics vs. FVC

If data lend themselves to it, additional exploratory analysis will be done to test for interaction between baseline characteristics (e.g., FVC/DLCO/6MWD) and change in FVC.

Exploratory analysis of PK/PD relationship

Descriptive statistics and correlation will be computed to explore the relationship of Pentraxin-2 levels vs FVC [% predicted]/FVC [ml]/slope of FVC ml at week 24 and 28, and the relationship of

Pentraxin-2 vs other PFTs/PROs/6MWT (Statistical table 14.2.26.1 and 14.2.26.2). If relevant the corresponding scatter plot will be produced.

Exploratory analysis of relationship between Pentraxin-2 levels and ADA

Correlation coefficient between Pentraxin-2 levels and ADA titer at week 28 will be computed (Statistical tables 14.2.27.1 and 14.2.27.2) and a scatterplot prepared (using logarithmic coordinates for titers).

Exploratory analysis of acute exacerbations

Tabulation of each type of acute exacerbations will be produced (Statistical table 14.2.28.1.1 and 14.2.28.1.2). Descriptive statistic and Kaplan-meier curve will be computed by treatment group for time to first reported acute exacerbation (Statistical tables 14.2.28.2.1 and 14.2.28.2.2).

Additional exploratory analysis: FVC [% predicted] separately on pirfenidone and nintedanib

The same model as the one for the primary analysis (see section 5.2.5.1) will be used separately on (i) patient on a stable dose pirfenidone and (ii) patient on a stable dose of nintedanib (Statistical table 14.2.20.1.1 to 14.2.20.2.2).

Additional exploratory analysis: time variation in historic FVC [% predicted; ml] measurements:

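### The SAP plans no count of patients who develop anti-drug antibodies and no rule for negative results, so seroconversion cannot be read from its ADA change table

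*SAP*

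**What the plan says.** Protocol section 1.5 states that the risks of PRM-151 "consist of potential development of anti-drug antibodies and infusion reactions", and adds that such antibodies might cross-react with the endogenous protein. On earlier experience it reports: "Anti-drug antibodies were detected in 3 subjects in the MF trial, with no apparent impact on pharmacokinetics, safety, or efficacy". Protocol section 1.2 reports no antibodies in the earlier IPF study.

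In the SAP, the post-baseline ADA summary sits in section 5.2.5.3 under exploratory objective EO2, on the ATS and PP sets. It has two parts: raw values at each visit, and "change from baseline to each visit in anti-Pentraxin-2 antibodies measurements will be computed by treatment group" (tables 14.2.22.1 and 14.2.22.2). Individual values go to Listing 16.2.6.8. Section 8 defines change for a continuous variable as the visit value minus the baseline value, with the reading "Negative values indicate a decrease in X". It has no derivation specific to ADA.

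ADA is at least partly a titre: "Correlation coefficient between Pentraxin-2 levels and ADA titer at week 28 will be computed". The accompanying scatterplot is drawn "using logarithmic coordinates for titers". The summary tables have no log-scale or geometric counterpart. The missing-data rule for the section is: "For all exploratory efficacy endpoints, the analyses will be based on observed data only", with nothing imputed.

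ADA appears in three other places. Section 5.2.1 tabulates it at baseline on the SAF, ATS and PP sets. Section 5.2.6.3 splits the infusion-reaction tables by ADA presence or absence. An additional exploratory FVC model in section 5.2.5.3 uses presence, level or both. Presence is not defined in any of these.

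**The concern.** When antibody formation is a named risk, the first figure a reader wants is how many patients in each arm were negative at baseline and positive later. The list of tables in SAP section 9.1 has no ADA incidence, shift or treatment-emergent table. The SAP defines treatment emergence only for adverse events (section 4.2.1). It does plan shift tables for laboratory tests and vital signs, and a count of patients above or below a threshold for the cough questionnaire.

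An arithmetic difference is a poor substitute. For a patient negative at baseline, its meaning depends on what number, if any, stands for a negative result, and the plan is silent on that. What is at stake is the reporting of one of the two risks named in protocol section 1.5. If the definitions are left open, the count would be defined after unblinding or left to a hand count from the listing.

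**Working it through.** The plan gives no figure to reproduce here. The check applies the section 8 formula under the two obvious codings of a negative result.

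**Inputs from the documents**
- PRM-151 arm: 78 patients (SAP 2.3.2).
- Change = visit value minus baseline value (SAP section 8).
- No imputation (SAP 5.2.5.3).
- Earlier ADA experience: 3 subjects. Section 1.5 gives safety data on 27 subjects with myelofibrosis but does not say that all 27 were tested.

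**Assumptions, for illustration only**
- 2 of the 78 are positive at baseline with an unchanged titre of 40.
- Every new positive has a titre of 160.
- Conversion rates are 5%, 11%, 20% and 30%, that is 4, 9, 16 and 23 of 78 patients.

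For context, 3/27 = 11.1%, with an exact 95% interval of 2.4% to 29.2%. Applied to 78 patients this is 78 × 3/27 = 8.7, with a range of about 2 (78 × 0.024) to 23 (78 × 0.292).

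**Coding A: a negative has no numeric value.** A new positive has a visit value and no baseline value, so the difference is missing. Only the 2 baseline positives have a change.

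**Coding B: a negative is stored as 0.** All 78 have a change. The mean is (number of new positives × 160)/78. The median is 0 whenever fewer than half have a non-zero change.

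| New positives | A: n in change table | A: new positives in it | A: n in raw-value table | B: n in change table | B: mean change | B: median |
|---|---|---|---|---|---|---|
| 4 | 2 | 0 | 6 | 78 | 8.2 | 0 |
| 9 | 2 | 0 | 11 | 78 | 18.5 | 0 |
| 16 | 2 | 0 | 18 | 78 | 32.8 | 0 |
| 23 | 2 | 0 | 25 | 78 | 47.2 | 0 |

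Under A the change table looks the same whether 4 or 23 patients convert.

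Under B the mean moves, but not with the count alone. Sixteen new positives at titre 160 give 16 × 160/78 = 32.8. Two new positives at titre 1280 give 2 × 1280/78 = 32.8. The mean and the median (0) are identical, with eight times as many converters in the first case.

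The quartiles help little. The upper quartile stays at 0 for 4, 9 and 16 converters and leaves 0 only at 23, once more than about a quarter of the arm has converted. The maximum shows that at least one patient converted, not how many.

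**The case against.** A reader might infer that the change from baseline is undefined for ADA-negative patients, and that those who develop antibodies therefore vanish from the report. The documents do not support that. The loss from the change table follows only if a negative has no numeric value, and neither document says so. A sample that was assayed and found negative is an observed result, and the rule against imputation does not by itself make it missing. Even under coding A, new positives remain in the raw-value table and in Listing 16.2.6.8.

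Other points on that side also stand:
- Mean change is not shown alone. SAP 5.1.1 adds the SD, median, quartiles and extremes, which would reveal a skewed titre distribution.
- If ADA status were handled as a qualitative variable, 5.1.1 would yield a number and percentage at each visit. The SAP does not say that it will be.
- The choice of ATS over SAF is minor. Sections 3.2 and 3.4 put the same patients in both, and the sets differ only in how a patient given the wrong treatment is allocated.
- The expected number of ADA-positive patients is weakly founded. Section 1.5 does not say that the 3 subjects were newly positive, and the earlier IPF study reported none.
- The analysis is descriptive and exploratory, and ADA is not among the protocol's listed safety endpoints.

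These points narrow the concern but do not answer it. Under coding A, the missing count in the raw-value table merges negative with not sampled. Under B, the raw-value table shows no count of positives. Under both it works visit by visit and does not link a patient's later status to baseline. The infusion-reaction split and the FVC model rest on an undefined presence, which could mean at baseline, at a visit, ever, or newly.

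**Conclusion.** The gap is real and limited. The SAP states no coding for ADA-negative results and plans no count of treatment-emergent ADA by arm. Seroconversion cannot be read from its change table under either coding examined. With negatives missing, 0 of 4, 9, 16 or 23 new positives appear there. With negatives at zero, all appear, but the median change is 0 throughout and the mean confounds how many converted with how high their titres were.

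The specific figures rest on assumed titres, two assumed baseline positives and assumed conversion rates. The structural result needs less: coding A removes any baseline-negative patient from the change table, and under B the median stays at 0 while fewer than half the arm has a non-zero change. Claims that antibody-positive patients disappear from the report, or that a given number of cases is to be expected, go beyond the documents.

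The effect is confined to exploratory and safety reporting. Alpha, power, sample size and the primary FVC analysis are untouched. The point still deserves correction before unblinding, because it concerns a risk that the protocol itself names.

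**What to change.** Amend SAP sections 5.2.5.3 and 8 and the 14.2.22 table shells before unblinding:

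1. State how an ADA-negative result is recorded, and keep it distinct from a sample not taken.
2. Define ADA-positive at baseline, treatment-emergent ADA (negative at baseline and positive at any later visit) and boosted ADA (positive at baseline with a titre rise above a threshold fixed before unblinding).
3. Replace the arithmetic change table with n/N (%) ADA-positive by arm and visit, and n/N (%) with treatment-emergent ADA by arm, presented on the SAF. Show boosted ADA separately.
4. Keep the raw-value summary, but report titres among positives as median, range and geometric mean.
5. Say which definition of presence applies in the infusion-reaction tables and the FVC model.

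The cost is SAP wording and one table shell. No new samples are needed: the schedule in protocol Appendix A already has ADA at baseline, Weeks 4 to 24 and Week 28.
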